**Table 4. Response determination for chronic GvHD**

Organ	Complete Response	Partial Response	Progression
Skin	NIH Skin Score 0 after previous involvement	Decrease in NIH Skin Score by 1 or more points	Increase in NIH Skin Score by 1 or more points, except 0 to 1
Eyes	NIH Eye Score 0 after previous involvement	Decrease in NIH Eye Score by 1 or more points	Increase in NIH Eye Score by 1 or more points, except 0 to 1
Mouth	NIH Modified OMRS 0 after previous involvement	Decrease in NIH Modified OMRS of 2 or more points	Increase in NIH Modified OMRS of 2 or more points
Esophagus	NIH Esophagus Score 0 after previous involvement	Decrease in NIH Esophagus Score by 1 or more points	Increase in NIH Esophagus Score by 1 or more points, except 0 to 1
Upper GI	NIH Upper GI Score 0 after previous involvement	Decrease in NIH Upper GI Score by 1 or more points	Increase in NIH Upper GI Score by 1 or more points, except 0 to 1
Lower GI	NIH Lower GI Score 0 after previous involvement	Decrease in NIH Lower GI Score by 1 or more points	Increase in NIH Lower GI Score by 1 or more points, except from 0 to 1
Liver	Normal ALT, alkaline phosphatase, and Total bilirubin after previous elevation of 1 or more	Decrease by 50%	Increase by 2 × ULN
Lungs	- Normal %FEV1 after previous involvement - If PFTs not available, NIH Lung Symptom Score 0 after previous involvement	- Increase by 10% predicted absolute value of %FEV1 - If PFTs not available, decrease in NIH Lung Symptom Score by 1 or more points	- Decrease by 10% predicted absolute value of %FEV1 - If PFTs not available, increase in NIH Lung Symptom Score by 1 or more points, except 0 to 1
Joints and fascia	Both NIH Joint and Fascia Score 0 and P-ROM score 25 after previous involvement by at least 1 measure	Decrease in NIH Joint and Fascia Score by 1 or more points or increase in P-ROM score by 1 point for any site	Increase in NIH Joint and Fascia Score by 1 or more points or decrease in P-ROM score by 1 point for any site
Global	Clinician overall severity score 0	Clinician overall severity score decreases by 2 or more points on a 0-10 scale	Clinician overall severity score increases by 2 or more points on a 0-10 scale

ULN indicates upper limit of normal.

- Resistance is defined as lack of a CR/PR 2 weeks after the last ATO infusion,

[figure not shown]
requirement for alternative therapy or death from GvHD before the last ATO infusion

- Treatment failure is defined as death, recurrent or progressive malignancy or the initiation of new systemic treatment for chronic GvHD. Increased dosing of existing treatment will not be considered as failure.

Indications for secondary systemic treatment of chronic GvHD:

Secondary systemic immunosuppressive treatment or other systemic treatment for control of chronic GvHD will be given at the discretion of the investigator in consultation with the GvHD team. In general, secondary systemic treatment is not indicated as long as there is continuing improvement in at least one manifestation of chronic GvHD and no progression of any other manifestations.

**Figure 1. Study plan of investigational product and secondary systemic treatment**

### Dose delay, modification and reinitiation

Treatment with ATO must be interrupted, adjusted, or discontinued before the scheduled end of therapy at any time that a toxicity grade 3 or greater, on the National Cancer Institute Common Toxicity Criteria, is observed and judged to be possibly related to ATO treatment. Patients who experience such reactions that are considered ATO related must resume treatment only after resolution of the toxic event or after recovery to baseline status of the abnormality that prompted the interruption. In such cases, treatment must resume at 50% of the previous daily dose. If the toxic event does not recur within 3 days of restarting treatment at the reduced dose, the daily dose can be escalated back to 100% of the original dose. Patients who experience a recurrence of toxicity must be removed from treatment.

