  - 0,15 mg/kg/infusion on days 1 to 5 (first week), 3 times per week during the second week (for example, days 8, 10 and 12), 2 times per week during the third week (for example, days 15 and 17) and one time during the fourth week (for example, day 24), in addition to ciclosporine A (if relevant) and corticosteroids. The latter four weeks represent one cycle of 11 administrations.
  - Must be administered intravenously over 1-2 hours. The infusion duration may be extended up to 4 hours if vasomotor reactions are observed. A central venous catheter is not required. Patients must be hospitalized at the beginning of treatment due to ensure adequate monitoring.
  - Aseptic technique must be strictly observed throughout handling of ATO since no preservative is present.

- Must be diluted with 100 to 250 mL of glucose 50 mg/mL (5%) solution for injection or sodium chloride 9 mg/mL (0.9%) solution for injection immediately after withdrawal from the ampoule for single use only. Unused portions of each ampoule must be discarded properly. Unused portions for later administration must not be saved.
- Must not be mixed with or concomitantly administered in the same intravenous line with other medicinal products.
- The diluted solution must be clear and colorless. All parenteral solutions must be inspected visually for particulate matter and discoloration prior to administration. The preparation must not be used if foreign particulate matter is present.
- Should be administered within 10 days of starting prednisone at 1mg/kg/day for cGvHD treatment. Treatment with persistent prednisone (or equivalent) at doses lower than 1 mg/kg/day at the time of enrollment is allowed (i.e patient was treated for acute GvHD with prednisone and developed evolving chronic GvHD).
- A delay of 8 weeks to a maximum of 11 weeks (from the first infusion of ATO) will be observed between the two cycles of ATO therapy.

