### ECG and Electrolyte Monitoring Recommendations

During therapy with ATO, potassium concentrations must be kept above 4 mEq/l and magnesium concentrations must be kept above 1.8 mg/dl. In case of increase of QTc > 500 msec (Summary of Product Characteristics (Trisenox)), syncope, rapid or irregular heartbeat development, the treatment is immediately interrupted and the patient must be hospitalized, the EKG monitored continuously, serum electrolytes assessed and a cardiological advice requested.

ATO therapy must be discontinued until the QTc interval regresses to below 460 msec, electrolyte abnormalities are corrected, the syncope and irregular heartbeat cease. In accordance with the Safety Committee, the treatment could be reinitiated after the validation of the posology.

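### For a possibly related grade 3 or higher event that is also a QTc, syncope or heartbeat trigger, protocol Section 7.3.2 gives two restart procedures and does not say how they combine

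*Protocol*

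**What the plan says.** Protocol Section 7.3.2 has two consecutive paragraphs on stopping and restarting ATO.

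*Dose delay, modification and reinitiation* (the general paragraph) applies whenever a "toxicity grade 3 or greater, on the National Cancer Institute Common Toxicity Criteria, is observed and judged to be possibly related to ATO treatment". Affected patients "must resume treatment only after resolution of the toxic event or after recovery to baseline status of the abnormality that prompted the interruption". The restart dose is then fixed: "In such cases, treatment must resume at 50% of the previous daily dose". Re-escalation is conditional: "If the toxic event does not recur within 3 days of restarting treatment at the reduced dose", then "the daily dose can be escalated back to 100% of the original dose". A recurrence takes the patient off treatment. The paragraph has no cardiac exception and names no decision-maker or committee.

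*ECG and Electrolyte Monitoring Recommendations* (the ECG paragraph) is triggered "In case of increase of QTc > 500 msec", or by syncope or a rapid or irregular heartbeat. It sets no toxicity grade and no relatedness condition. ATO is stopped and the patient is admitted. ATO stays off until QTc is under 460 msec, electrolytes have been corrected and the symptoms have ended. Restart is then optional: "In accordance with the Safety Committee, the treatment could be reinitiated after the validation of the posology". The paragraph states no dose, no re-escalation step and no rule for recurrence.

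Neither paragraph refers to the other. The SAP has no dose-modification rule that settles the matter. SAP Section 11.3.1 only describes the doses given and any temporary discontinuation.

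**The concern.** An event can meet both triggers. For it, the two paragraphs differ on when ATO may restart, how the restart dose is set and whether the Safety Committee must agree. A site that applies the general paragraph as written could restart, and later re-escalate, after a serious cardiac event without the committee step that the ECG paragraph calls for.

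The overlap is foreseeable. Protocol Section 1.3 puts QT prolongation among the most serious effects of ATO, and Section 11.8 says it can lead to a fatal arrhythmia. Section 10.6 sets no early stopping criterion, so the patient-level rules carry more of the protection. Eleven sites are planned for 24 patients, which leaves room for different practice after the same event.

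There is also a practical reason to fall back on the general paragraph. Section 11.9 describes the committee as a trial-level body that meets periodically, and gives no procedure for validating one patient's dose.

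**Working it through.** This is a comparison of texts with one threshold check. The plan states no statistical figure to reproduce.

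**1. Which events fall under both paragraphs.** The event must be (a) grade 3 or higher, (b) judged possibly related to ATO, and (c) an ECG-paragraph trigger. Below grade 3, or if judged unrelated, only the ECG paragraph applies.

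**2. The two paragraphs side by side for such an event.**

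| Item | General paragraph | ECG paragraph |
|---|---|---|
| Condition for restart | Resolution, or return to baseline; no QTc value | QTc below 460 msec, electrolytes corrected, symptoms ended |
| Restart dose | 50% of the previous dose, compulsory | None stated; to be validated |
| Who agrees | Nobody named | Safety Committee |
| Re-escalation | To 100% if no recurrence within 3 days | Not addressed |
| Recurrence | Removal from treatment | Not addressed |

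**3. Can the timing conditions disagree?** Protocol Section 4.2 excludes QTc above 450 msec in men and above 470 msec in women. The highest eligible baselines are therefore 450 and 470 msec, to be compared with the restart threshold of below 460 msec. I take baseline to be the screening value and all values to use one correction formula.

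- Man, baseline at most 450, QTc falls to 451-459. This is below 460, so the ECG paragraph's QTc condition is met. It is above 450, so he is not back at baseline. At the eligibility limit the gap is up to 459 - 450 = 9 msec.
- Woman, baseline 460-470, QTc returns to baseline. The baseline condition is met. Her QTc is not below 460, so the ECG paragraph's condition is not. With a baseline of 470 she would have to fall more than 470 - 460 = 10 msec below her own baseline.

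So neither condition is uniformly the stricter one. The general paragraph's other route, resolution, has no QTc value attached, so it does not settle either case.

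**4. The 3-day window.** Infusions are daily only in week 1. By week 4 the schedule is "and one time during the fourth week (for example, day 24". The text does not say how three days without recurrence are to be counted when infusions are not daily.

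**The case against.** The strongest reply is that this is an ordinary general rule followed by a specific one. The ECG paragraph names its events, Section 13.1 requires the protocol to be followed strictly, and the two paragraphs can be applied cumulatively. If the committee validates a 50% restart, both are satisfied on dose. This stands as a possible reading. It is not stated, and it leaves open which recovery condition binds and whether the 3-day re-escalation also needs the committee.

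A reader might infer more than the documents support:

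- *That the section prescribes two conflicting doses.* It does not, because the ECG paragraph gives no dose.
- *That the general paragraph compels a return to the exact baseline QTc.* It does not, because resolution is an alternative.
- *That it leaves the decision to the investigator.* It names nobody, and silence does not contradict the committee step.
- *That a daily dose makes no sense when infusions are not daily.* SAP Section 11.3.1 divides the total dose by the number of treatment days, so the term can be read as dose per infusion day.
- *That the number of reduced infusions before re-escalation can be read off the example calendar.* Section 7.3.2.1 calls the plan indicative and moves cancelled infusions, so spacing after a restart is unknown.

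The CTC grades are not reproduced in the supplied text. That limits how large the overlap can be said to be, but does not remove it.

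**Conclusion.** The point holds in a limited form. For events that are grade 3 or higher, possibly related and also an ECG-paragraph trigger, Section 7.3.2 gives two restart procedures with different recovery conditions, different ways of setting the dose and different authority. No precedence is stated in the protocol or SAP. The recovery conditions can disagree in both directions at QTc values the eligibility criteria allow. The dose given may depend on the paragraph a site applies, but the documents do not show that it must.

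The size of the overlap rests on an assumption about grading. If every QTc above 500 msec is grade 3 or higher, all such events judged possibly related are affected. If none is, the overlap is confined to syncope and heartbeat events that reach grade 3. The number of patients affected cannot be estimated from the documents. This is a wording defect in a safety rule that should be corrected. It does not bear on the sample size or the primary analysis.

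**What to change.** Reconcile the two paragraphs of Section 7.3.2 by cross-reference. State whether they apply together to these events or which one governs, so that a site finds one recovery condition, one way of setting the restart dose and one decision-maker. If the Safety Committee's agreement is required for an individual patient, say how it is obtained between its periodic meetings. State also how the 3-day re-escalation window is counted when infusions are not daily, and whether re-escalation and the recurrence rule apply after a restart under the ECG paragraph.

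The sponsor and Safety Committee decide the content. No dose or clinical rule is proposed here.

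The cost is a protocol wording amendment, with the notification or approval that Section 13.1 requires. It needs no extra patients or data, since Table 2 already provides for recording ATO dates, doses and reasons for change.

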### ECG and Electrolyte Monitoring Recommendations

During therapy with ATO, potassium concentrations must be kept above 4 mEq/l and magnesium concentrations must be kept above 1.8 mg/dl. In case of increase of QTc > 500 msec (Summary of Product Characteristics (Trisenox)), syncope, rapid or irregular heartbeat development, the treatment is immediately interrupted and the patient must be hospitalized, the EKG monitored continuously, serum electrolytes assessed and a cardiological advice requested.

ATO therapy must be discontinued until the QTc interval regresses to below 460 msec, electrolyte abnormalities are corrected, the syncope and irregular heartbeat cease. In accordance with the Safety Committee, the treatment could be reinitiated after the validation of the posology.

## 8. Examinations and evaluations

### 8.1. Calendar of evaluations

The total length of follow up period for this protocol will be for 12 months following the first infusion of ATO, with a first follow up at 6 and 14 weeks, then at 6, 9 and 12 months post-inclusion.

In case of postponement of several administrations of Arsenic trioxide or second cycle of treatment, the visit of follow up must also be postponed to respect the 2 weeks delay after the end of the cycle (for 6 and 14 weeks only).

### 8.2. Evaluations during treatment with ATO

The following evaluations must be performed:

- Before each administration of ATO during the first and the second cycle (if applicable):
  - Physical examination, including vital signs
  - EKG with measurement of the QTc interval according to the formula in Section 11.8
  - Serum chemistries: calcium, potassium, magnesium, creatinine
  - Collection of whole blood (5 mL) for pharmacokinetic assessment (see Section 8.4)
- At time of treatment initiation each week (for example days 1, 8, 15 and 24):
  - Physical examination, including vital signs, weight
  - GvHD assessment
  - Monitoring and recording of treatment associated, particular attention must be paid to drugs reported to prolong QT interval and/or induce torsade de pointes (see Appendix 7)
  - EKG with measurement of the QTc interval according to the formula in Section 11.8
  - Serum chemistries: potassium, magnesium, creatinine, uric acid, total bilirubin, alkaline phosphatases, LDH, total protein, albumin, SGOT (ASAT) and SGPT (ALAT) (twice a week), calcium, glycaemia (twice a week)
  - Hematology: complete blood count (CBC) with differential counts (twice a

week)

- Coagulation test with measurement of PT and APTT (twice a week)
- Infectious disease surveillance: CMV, EBV as per centre practice (and Hep B surface Ag, Hep B surface antibody if relevant)
- Monitoring the kinetics of certain autoantibodies [antinuclear antibody (AAN), anti-neutrophil cytoplasmic antibody (ANCA)]
- Collection of whole blood (5 mL) for pharmacokinetic assessment (see Section 8.4)
- Collect of whole blood (35 mL) for immunological evaluations ((see Section 8.3)

### **8.3. Surveillance post-treatment with ATO**

➤ Participation in this study should not substantially modify the clinical and biological surveillance of this type of patients with chronic GvHD. The monitoring and evaluation timetable are outlined in the appendices.

➤ Clinical monitoring performed weekly during the first month of ATO therapy, then twice a month up to three months, and then on a monthly basis during six months, and then on a trimester basis at 9, 12 months (whenever possible no more than +/- 5 days before or after calculated visit date allowed):

Note : if a second cycle needed, the corresponding follow-up visit Week 8 becomes optional because it is very close to the first visit of the second cycle (Week 9)

- Physical examination
- GvHD assessment
- Documentation of daily steroid dose
- Monitoring and recording of all adverse events (AEs) and therapeutic measures taken (medications and other significant interventions) during all the study
- Documentation of any associated treatments and topical therapy for chronic GvHD (including glucocorticoid creams, topical tacrolimus, oral beclomethasone or budesonide, topical azathioprine and ophthalmic glucocorticoids...)
- Documentation of disease progression or relapse

- Documentation of any introduction of new systemic therapy
- Evaluation of GvHD using the chronic GvHD Activity Assessment-Clinician Form A (see below and Appendix 8) at 6 and 14 weeks, and at 6, 9 and 12 months
- Biological monitoring performed weekly or twice weekly (according to the parameters) during the first month of ATO therapy, then twice a month up to three months, and then on a monthly basis during 6 months, and a trimester basis at 9 and 12 months
- Hematology: complete blood count (CBC) with differential counts
- Coagulation test with measurement of PT and APTT
- Serum Chemistries: potassium, magnesium, creatinine, uric acid, total bilirubin, alkaline phosphatase, LDH, total protein, albumin, SGOT (ASAT), SGPT (ALAT), calcium
- Infectious disease surveillance: CMV, EBV as per centre practice (and Hep B surface Ag, Hep B surface antibody if relevant)
- Serum immunoglobulin levels will be measured at baseline entry on the study and monthly per centre practice. Repletion of intravenous immunoglobulin (IVIG) is advised for patients with recurrent infections or IgG levels <400 mg/dL
- Monitoring the kinetics of certain autoantibodies [antinuclear antibody (AAN), anti-neutrophil cytoplasmic antibody (ANCA)]

➤ Immunological evaluations:

- Given the apoptotic effects of ATO on the immune system, and as a secondary endpoint, this protocol will include some immunological evaluations at inclusion, at one, 3, 6 and 14 weeks (at 9, 10 and 12 weeks in case of second treatment cycle) and at 6 months and later at 9 and 12 months (as described in the protocol flow-chart), aiming to assess the immune effects of the drug.
- Therefore, peripheral blood samples (30 mL on heparin tubes) and serum (5 mL) at each time point will be drawn to assess allogeneic and protective antibody responses prior to and after ATO therapy : at one week (W1D1), at second and fourth week (W2D8 and W4D24), at evaluation visits 6 et 14 weeks (at 9, 10 and 12 weeks in case of second treatment cycle) and at 6 months and later at 9 and 12 months (as described in the protocol flow-

chart),:

- To evaluate the effect of ATO on the oxidative stress pathway:  
Evaluation of the circulating level of ROS using the free oxygen radicals test (FORT)
- To decipher the relation between dendritic cells, in particular plasmacytoid dendritic cells, helper T cells (Th1, Th2, Th17) and follicular helper T cells and B cells in the context of chronic GvHD under treatment by ATO:  
Peripheral blood mononuclear cells (PBMC) phenotype and immunophenotype  
RNA sequencing of sorted CD4+ lymphocytes and dendritic cells to evaluate the effect of ATO on cell signaling  
Circulating level of Th1, Th2 and Th17 related cytokines
- Evaluate the effect of ATO on T cells and B cells diversity (if relevant)  
T-cell receptor (TCR) and B-cell receptor (BCR) sequencing

Immunological evaluations are centralized at Saint-Antoine Hospital (Paris, France). The whole blood samples of patients (except for patients included at Hôpital Saint-Antoine) will be shipped within 24 hours to the Hôpital Saint-Antoine, at room temperature by a carrier. The serum of patients are frozen at -80°C and should be globally sent at the end of each cycle or at the end of study by a carrier.

- Quality of life parameters:
  - Quality of life questionnaire at inclusion (LSS and FACT-BMT), at 6 and 14 weeks, and 6, 9 and 12 months (LSS and FACT-BMT) (see Appendix 10 to Appendix 11)
- Tumor response assessment:
  - These examinations will be made depending on the type of the underlying disease and according to each centre practice.

#### **8.4. Pharmacokinetic measurement**

A sample of 5 mL of whole blood on heparin tube will be taken before each administration at D2, D3, D4, D5, D8, D12, D17 and D24 of cycle 1 and cycle 2 (if

applicable). Plasma and red cells will be harvested and frozen at -20°C or -80°C and should be globally carried by a professional carrier at the end of each cycle or at the end of study to the Lariboisière laboratory ([name]).

Determination of plasma and erythrocyte arsenic

Blood will be drawn on heparin tube. At arrival at the laboratory, the blood will be centrifuged and the plasma will be separated from blood cells. The arsenic dosage is determined in the plasma and red blood cells by spectrometry in inductively coupled plasma mass spectrometers (ICP-MS) on Elan DRCE (Perkin Elmer) equipped of a reaction cell. In this technique, the pre-diluted sample will be sent in aerosol form in argon plasma of which temperature is about 8,000 K. All the species present in the sample are then reduced to the state of atom, mostly in ionized form.

The ions formed are then extracted from the plasma and introduced into the reaction cell, and then, in the mass spectrometer which separates the ions according to their mass to charge ratio. At the output of the mass spectrometer, a sensor counts the number of ions given mass (Poupon J, 2008). As the arsenic contains only a mass 75 isotope ( $^{75}\text{As}$ ) interfered by  $^{40}\text{Ar}^{35}\text{Cl}$ , oxygen will be used as the reaction gas for forming the read 91 AsO mass free of interference. Internal quality controls (Seronorm® serum levels 1 and 2, Seronorm® whole blood levels 1, 2 and 3, Sero, distributed by Ingen) will be analyzed in each series. The detection limit will be 1 nmol L (0.001 mol/L) in the serum.

After analysis, the samples will be stored at -40 ° C until the end of the study.

